I agree to maintain all study related information supplied by Biosense Webster, Inc. in strictest confidence. When information regarding this study is submitted to an institutional review board (IRB)/Independent Ethics Committee (IEC), it will be forwarded with a requirement that all study related material is to be held strictly confidential.

Principal Investigator
Name (PRINT)

Signature

Date

Protocol Summary

Prospective Revue of the Safety and Effectiveness of the THERMOCOOL SMARTTOUCH[®] SF Catheter Evaluated for Treating Symptomatic Persistent AF (PRECEPT)

- Title:** Prospective Revue of the Safety and Effectiveness of the THERMOCOOL SMARTTOUCH[®] SF Catheter Evaluated for Treating Symptomatic Persistent AF (PRECEPT)
- Design:** This is a prospective, multicenter, non-randomized clinical evaluation utilizing the THERMOCOOL SMARTTOUCH[®] SF catheter compared to a predetermined performance goal.
- Purpose:** The purpose of this study is to demonstrate the safety and effectiveness of the THERMOCOOL SMARTTOUCH[®] SF catheter in the treatment of drug refractory symptomatic persistent atrial fibrillation (PsAF) following standard electrophysiology mapping and RF ablation procedures.
- Enrollment:** Up to 367 subjects will be enrolled.
- Clinical Sites:** Up to 35 sites (approximately 30 in the US and up to 5 OUS).
- Subject Population:** Subjects with drug refractory symptomatic PsAF who are undergoing their first AF ablation procedure that meet the ACC/ESC/HRS criteria for persistent AF are eligible.
- Primary Endpoints:** The primary effectiveness endpoint for this study will be freedom from documented atrial fibrillation (AF), atrial tachycardia (AT), or atrial flutter (AFL) episodes through 15-month follow-up (post 3-Month Medication Adjustment Period followed by a 3-Month Therapy Consolidation period (Day 181-450)).
- The primary safety endpoint is the incidence of any early onset (within 7 days of the initial and repeat AF ablation procedure) Primary Adverse Events (AE), which are listed below:
- Death
 - Atrio-esophageal fistula*
 - Cardiac Tamponade**†/Perforation⁺
 - Myocardial infarction (MI)
 - Stroke / Cerebrovascular accident (CVA)^{†, ††}
 - Thromboembolism
 - Transient Ischemic Attack
 - Diaphragmatic paralysis
 - Pneumothorax
 - Heart block
 - PV stenosis*
 - Pulmonary edema (Respiratory Insufficiency)
 - Pericarditis
 - Major Vascular access complication / bleeding
- * Pulmonary vein (PV) stenosis and atrio-esophageal fistula that occurs greater than one week (7 days) post-procedure shall be deemed Primary AEs.
- ** Hemodynamic compromise or instability is defined as Systolic BP < 80 mm Hg.
- + Cardiac Tamponade/Perforation that occurs up to 30 days post ablation will be deemed Primary AEs.
- † Subjects with non-focal global encephalopathy will not be reported as a stroke without unequivocal evidence based upon neuroimaging studies.

†† Modified Rankin score assessments should be made by qualified individuals according to a certification process.
If there is discordance between the 30 and 90 day Modified Rankin scores, a final determination of major versus minor stroke will be adjudicated by the neurology members of the Global Safety Monitoring Committee.

Sponsor: Biosense Webster, Inc.
[name]
[name] USA

List of Abbreviations

AAD	Antiarrhythmic drug	ICF	Informed consent form
ACC	American College of Cardiology	IDE	Investigational device exemption
ACT	Activated clotting time	IEC	Independent Ethics Committee
AE	Adverse event	IFU	Instructions for use
AF	Atrial fibrillation	IRB	Institutional Review Board
AFEQT	Atrial Fibrillation Effect on QualiTy of life	ITT	Intent-to-treat
		HIPAA	Health Insurance Portability and Accountability Act
AFL	Atrial flutter		
AHA	American Heart Association	LA	Left atrium
ANOVA	Analysis of variance	MI	Myocardial infarction
AT	Atrial tachycardia	MRI	Magnetic resonance imaging
AV	Atrioventricular	MV	Mitral valve
BP	Blood pressure	NIHSS	NIH Stroke Scale
CCS-SAF	Canadian Cardiovascular Society Severity of Atrial Fibrillation scale	PCI	Pecutaneous coronary intervention
		PIU	Patient Interface Unit
CHF	Congestive heart failure	PP	Per protocol
CF	Contact force	PsAF	Persistent atrial fibrillation
CFAE	Complex fractionated atrial electrogram	PV	Pulmonary vein
		PVI	Pulmonary vein isolation
CHADS	C ongestive heart failure, H igh blood pressure, A ge 75+, D iabetes, previous S troke or transient ischemic attack	PRECEPT	P rospective R ewiew of the Safety and E ffectiveness of the SMARTTOUCH® SF C atheter E valuated for Treating Symptomatic P ersistent A F
CPVI	Complete pulmonary vein isolation		
CRF	Case Report Form	QOL	Quality of life
CS	Coronary sinus	RA	Right atrium
CT	Computed tomography	RF	Radiofrequency
CTI	Cavotricuspid isthmus	SAC	Study advisory committee
CVA	Cerebrovascular accident	SADE	Serious adverse device effect
ECAS	European Cardiac Arrhythmia Society	SAE	Serious adverse event
ESC	European Society of Cardiology	SAP	Statistical analysis plan
FDA	Food Drug Administration	SF	Surround Flow
GCP	Good Clinical Practice	SVC	Superior vena cava
ECG	Electrocardiogram	TIA	Transient ischemic attack
EHRA	European Heart Rhythm Association	TEE	Transesophageal echocardiogram
GSMC	Global Safety Monitoring Committee	TTE	Transthoracic echocardiogram
HRS	Heart Rhythm Society	TTM	Transtelephonic monitoring
ICD	Implantable cardioverter defibrillator	UADE	Unanticipated adverse device effect
ICE	Intracardiac echocardiography	USADE	Unanticipated serious adverse device effect
		VT	Ventricular tachycardia

Prospective Review of the Safety and Effectiveness of the THERMOCOOL SMARTTOUCH® SF Catheter Evaluated for Treating Symptomatic Persistent AF (PRECEPT)

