4.1.2 Primary Safety Endpoint

The primary safety endpoint is the incidence of any primary adverse event occurring within 7 days of the AF ablation procedure (including the initial and repeat procedures) using the study catheter per protocol.

Primary adverse events include the following conditions (refer to Table 6-1 Primary Adverse Events for detailed instructions for defining these adverse events):

- Death
- Atrio-esophageal fistula*
- Cardiac Tamponade**+/Perforation⁺
- Myocardial infarction (MI)
- Stroke / Cerebrovascular accident (CVA) †, ††
- Thromboembolism
- Transient Ischemic Attack
- Diaphragmatic paralysis
- Pneumothorax
- Heart block
- PV stenosis*
- Pulmonary edema (Respiratory Insufficiency)
- Pericarditis
- Major vascular access complication / bleeding

* Pulmonary vein (PV) stenosis and atrio-esophageal fistula that occurs greater than one week (7 days) post-procedure shall be deemed Primary AEs.^{47,48}

** Hemodynamic compromise or instability is defined as Systolic BP < 80 mm Hg.

+ Cardiac Tamponade/Perforation occurring within 30 days of the AF ablation process will be considered Primary AEs

† Subjects with non-focal global encephalopathy will not be reported as a stroke without unequivocal evidence based upon neuroimaging studies.

†† Modified Rankin score assessments should be made by qualified individuals according to a certification process. If there is discordance between the 30 and 90 day Modified Rankin scores, a final determination of major versus minor stroke will be adjudicated by the neurology members of the GSMC.

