6.0 ADVERSE EVENTS

6.1 Adverse Event Recording

An Adverse Event is any untoward medical occurrence, unintended disease or injury, or untoward clinical signs (including abnormal laboratory findings) occurring during a clinical study, whether related to the study device or ablation procedure.

Adverse events will be collected from signing of informed consent throughout study follow-up, at each evaluation and whenever the physician becomes aware of an event. Investigators will determine, at each encounter, whether any adverse events (AE) have occurred, and judge their seriousness and relationship to the study device and procedure.

All adverse events, regardless of classification, seriousness, intensity, outcome, or causality, must be recorded in the electronic CRF(s) in a timely manner throughout the study. Onset date of the event, its treatment, current status (resolved, stabilized, or ongoing), and assessment of its seriousness and relationship to the device should be provided when available. All AEs will be monitored until they are resolved or stabilized (no further changes anticipated).

AF recurrence by itself is considered a recurrence of disease (pre-existing condition), and, therefore, does **not** meet the definition of an AE. Recurrence of pre-existing AFL/AT is also considered recurrence of disease, and not an AE.

The following additional clinical events will not be considered adverse events for this clinical study:

- Minor pericarditis attributable to the ablation procedure defined as pleuritic chest discomfort with or without pericardial rub and ECG changes.
- A trace / trivial / minor pericardial effusion that is asymptomatic, requires no medical intervention, and does not extend hospitalization will not be considered an adverse event.
- AF/AFL/AT recurrence requiring pharmacological or synchronized electrical cardioversion during the hospitalization for the index ablation procedure, or throughout the duration of the study.
- Reablation for AF or pre-existing AFL/AT.

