6.2.1 Primary Adverse Event

A Primary AE is one of the following events occurring within seven (7) days following an AF ablation procedure with the study catheter:

Table 6-1 Primary Adverse Events

PRIMARY ADVERSE EVENT	DESCRIPTION / CRITERIA
Death	Patient death directly related to the device or procedure and occurs at any time during or after the procedure.
Atrio-Esophageal Fistula*	Is defined as a connection between the atrium and the lumen of the esophagus. Evidence supporting this diagnosis includes documentation of esophagus erosion combined with evidence of a fistulous connection to the atrium such as air emboli, an embolic event, or direct observation at the time of surgical repair. A CT or MRI scan is the most common method of documentation of an atrio-esophageal fistula.
Cardiac Tamponade***/Perforation⁺	The development of a significant pericardial effusion during or within 30 days of undergoing an AF ablation procedure. A significant pericardial effusion is one which results in hemodynamic compromise, requires elective or urgent pericardiocentesis, or results in a 1 cm or more pericardial effusion as documented by echocardiography. Cardiac tamponade should also be classified as "early" or "late" depending on whether it is diagnosed during or following initial discharge from the hospital.
Myocardial Infarction	The presence of any one of the following criteria: 
 • Detection of ECG changes indicative of new ischemia (new ST-T changes or new LBBB) which persists for more than 1 h • Development of a new pathological Q waves on an ECG, and • Imaging evidence of new loss of viable myocardium or new regional wall motion abnormality
Stroke⁵⁸	

PRIMARY ADVERSE EVENT	DESCRIPTION / CRITERIA

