6.11 Causality

Cause of AEs is defined as follows:

Table 6-5 Adverse Event Causality Classifications

Device Relationship	
Definitely Device-Related	The THERMOCOOL SMARTTOUCH® SF catheter directly caused or contributed to the AE.
Possibly Device-Related	The THERMOCOOL SMARTTOUCH® SF catheter may have caused or contributed to the AE.
Not Device-Related	The AE is not associated with the THERMOCOOL SMARTTOUCH® SF catheter.
Procedure Relationship	
Definitely Procedure-Related	The AE is directly associated by timing and/or pathophysiology with the standard electrophysiology or AF ablation procedure described in this protocol.
Possibly Procedure-Related	The AE may be associated by timing and/or pathophysiologic with the standard electrophysiology procedure described in this protocol.
Not Procedure Related	The AE is not associated with the AF procedure described in this protocol.

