### 6.1.2 Primary Safety Endpoint

The primary safety endpoint is the incidence of any primary adverse event (PAE) occurring within 7 days of the AF ablation procedure (including the initial and repeat procedures) using the study catheter per protocol.

The null and alternative hypotheses are:

*Hypothesis:*  $H_0: P_S \geq 0.16$

$H_a: P_S < 0.16$

where  $P_S$  is the proportion of subjects with the early onset (within seven days of the initial and repeat ablation procedure for AF) primary AE

PAEs include the following conditions:

 
• Death
 
• Atrio-esophageal fistula*
 
• Cardiac Tamponade**/Perforation†
 
• Myocardial infarction (MI)
 
• Stroke / Cerebrovascular accident (CVA)†,††
 
• Thromboembolism
 
• Transient Ischemic Attack
 
	
 
• Diaphragmatic paralysis
 
• Pneumothorax
 
• Heart block
 
• PV stenosis*
 
• Pulmonary edema (Respiratory Insufficiency)
 
• Pericarditis
 
• Major vascular access complication / bleeding
 

---	--

- \* Pulmonary vein (PV) stenosis and atrio-esophageal fistula that occurs greater than one week (7 days) post-procedure shall be deemed Primary AEs.
- \*\* Hemodynamic compromise or instability is defined as Systolic BP < 80 mm Hg.
- + Cardiac Tamponade/Perforation occurring within 30 days of the AF ablation process will be considered Primary AEs
- † Subjects with non-focal global encephalopathy will not be reported as a stroke without unequivocal evidence based upon neuroimaging studies.
- †† Modified Rankin score assessments should be made by qualified individuals according to a certification process. If there is discordance between the 30 and 90 day Modified Rankin scores, a final determination of major versus minor stroke will be adjudicated by the neurology members of the Global Safety Monitoring Committee (GSMC).

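### Death is an unconditional Primary AE in the Summary and SAP 6.1.2, but Table 6-1 counts only directly related death, at any time, and never ties that phrase to the causality grades

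*Protocol*

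**What the plan says.** The Protocol Summary lists the components of the primary safety endpoint as early-onset events, "within 7 days of the initial and repeat AF ablation procedure) Primary Adverse Events (AE), which are listed below". Death is a one-word item there, with no footnote.

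Protocol 4.1.2 states: "The primary safety endpoint is the incidence of any primary adverse event occurring within 7 days of the AF ablation procedure". It also lists Death as a bare item, but tells the reader to "refer to Table 6-1 Primary Adverse Events for detailed instructions for defining these adverse events".

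SAP 6.1.2 introduces its list with "PAEs include the following conditions", gives Death unqualified, and does not mention Table 6-1. SAP 9.2 sends the reader to Protocol 4.1 only for the justification of the performance goal.

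Table 6-1 (Protocol 6.2.1) opens with "A Primary AE is one of the following events occurring within seven (7) days following an AF ablation procedure with the study catheter". Its Death row then reads: "Patient death directly related to the device or procedure and occurs at any time during or after the procedure".

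Relatedness is graded in Table 6-5 (Protocol 6.11) as Definitely, Possibly or Not related, separately for device and procedure. The word directly occurs only in the two Definitely grades. The Possibly grade for the procedure reads: "The AE may be associated by timing and/or pathophysiologic with the standard electrophysiology procedure described in this protocol". Under Protocol 6.1, investigators "judge their seriousness and relationship to the study device and procedure".

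**The concern.** One component of a tested primary endpoint has two possible numerators. A programmer working from SAP 6.1.2 counts every death within 7 days of a procedure. A coder working from Table 6-1 counts only deaths that someone has judged directly related, and has no rule for turning the Table 6-5 grades into that judgement.

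The trial is single-arm and unblinded (SAP sections 3 and 4), and the relatedness call starts with the treating investigator. Much of the serious part of the composite works differently. In Table 6-1, MI, stroke, TIA, thromboembolism and pulmonary edema carry no condition of relatedness to device or procedure. A stroke on Day 3 counts whatever caused it, while a death on Day 3 may not.

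The same row also leaves the time window unclear. It says that death counts at any time, under a lead-in of seven days. Unlike fistula, PV stenosis and tamponade, Death has no footnote extending its window. Table 6-1 can therefore drop early deaths and, on one reading, add late ones.

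At stake is whether the primary safety result could show no deaths although one occurred within a week of ablation, and whether the component is fixed before the data are seen.

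**Working it through.** **1. The definitions side by side.** Take a subject who dies with no other Primary AE. Days are counted from the most recent procedure with the study catheter.

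| Death | Summary or SAP 6.1.2 read alone | Table 6-1 |
|---|---|---|
| Day 3, rated Definitely related | counts | counts |
| Day 3, rated Possibly related | counts | not settled: directly related is not mapped to this grade |
| Day 3, rated Not related | counts | excluded |
| Day 20, rated Definitely related | does not count | counts if the row overrides the lead-in; otherwise not |

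Three of the four cases differ or can differ.

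**2. The plan's own safety figure.** Inputs (Protocol 7.2.2 and 7.5, SAP 9.2): goal 16%, expected rate 8%, two-sided 5%, exact binomial, n = 232, at least 90% power. The test passes with x events if the upper limit U is below 0.16, where U solves P(X ≤ x | n, U) = 0.025.

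At n = 232 the largest passing count is 26, with type I error P(X ≤ 26 | 0.16) = 0.0247 and power P(X ≤ 26 | 0.08) = 96.8%. The claim of at least 90% power is true, but 232 is not the minimum: exact power first reaches 90% at n = 173 and stays there from n = 188. Nothing below depends on how 232 was derived.

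**3. Effect of one death on the rate.** The change is 1/n: 1/367 = 0.27 points, 1/330 = 0.30 points, 1/232 = 0.43 points. The sizes are planned enrolment, the effectiveness requirement and the safety requirement; the actual safety population is not known in advance.

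**4. Effect at the decision boundary.**

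| n | Largest passing count | Upper limit | One more event | Upper limit |
|---|---|---|---|---|
| 232 | 26 | 15.99% | 27 | 16.48% |
| 330 | 39 | 15.80% | 40 | 16.14% |
| 367 | 44 | 15.76% | 45 | 16.06% |

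**5. Effect near the expected 8%.** At 26/330 (7.88%) the upper limit is 11.33%. Adding 1, 2 or 3 deaths gives 11.68%, 12.03% or 12.38%. At 29/367 (7.90%) the limit is 11.15%, and three added deaths give 12.09%. Reaching failure from these counts takes 40 − 26 = 14 or 45 − 29 = 16 further events.

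**6. Effect on power.** The component rates behind the 8% (Table 4-1) are redacted, so the contribution of all-cause death is an assumption. If it adds 0.1 to 1.0 points to a true rate of 8%, power at n = 330 falls from 99.4% to between 99.3% and 96.6%. At n = 232 it falls from 96.8% to between 96.3% and 89.8%.

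**The case against.** The strongest reply is that these are labels with a definition behind them. Section 4.1.2 brings in Table 6-1 by reference, and other components are narrowed there too: pneumothorax needs a chest tube or surgery, and PV stenosis must be severe or symptomatic. This stands for Section 4.1.2. A reader might infer that 4.1.2 flatly contradicts Table 6-1, and the text does not support that. The reply is weaker for the Summary and for SAP 6.1.2, neither of which cites the table, and it does not supply the missing link to Table 6-5.

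A reader might also infer that Death is the only component exposed to a causal judgement. It is not. Heart Block in Table 6-1 requires an iatrogenic cause, and the stroke and pulmonary edema entries exclude certain alternative diagnoses, though not by relatedness to device or procedure.

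Independent review is a partial safeguard. Protocol 6.13 sends Primary AEs, and SAEs of cardiac origin within 30 days, to the GSMC. But no section gives that committee the task of adjudicating the relatedness of deaths, and a death judged both unrelated and non-cardiac may not reach it.

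Nor would an excluded death vanish. Any death on study is reported immediately (Protocol 6.2), and it remains an SAE, summarised with exact intervals and by causality (SAP 10.5.2.1). That summary is descriptive, however, and its 7-day window runs from the initial ablation. A death soon after a repeat procedure would usually fall in a later SAE window.

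Finally, the endpoint is a proportion of subjects, so a death that follows tamponade, stroke, MI or another Primary AE already counts through that event. This stands and limits the effect.

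**Conclusion.** The point holds as an ambiguity in a primary endpoint component. A death within 7 days rated not related counts if the SAP is read alone and is excluded under Table 6-1. One rated possibly related counts in the SAP and can be excluded under Table 6-1. It would go too far to say that a possibly related death is certainly excluded, because the documents do not settle that case.

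The numerical effect is small: 0.27 points per death at n = 367, only for deaths with no other Primary AE. The verdict changes only at the boundary (44 versus 45 of 367; 39 versus 40 of 330) and not near the expected 8%. A reader might infer that the safety conclusion is at risk; the figures do not support that unless the count is already at the limit. The number of such deaths is unknown, since the expected death rate is redacted.

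The case for acting is that the tested endpoint should have one definition before analysis, and its most severe component should not depend on an undefined attribution made without blinding.

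**What to change.** Use one definition of Death in the Summary, Protocol 4.1.2, Table 6-1 and SAP 6.1.2: any death within 7 days of an initial or repeat procedure with the study catheter is a Primary AE, whatever the attributed cause.

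In the same edit, reconcile the open-ended timing in the Table 6-1 row with the seven-day window. State explicitly whether related deaths after Day 7 also count, so that the new wording does not silently remove them. If they count, add a footnote like those for fistula, PV stenosis and tamponade, and name the Table 6-5 grades that qualify as related. Add a pointer to Table 6-1 in SAP 6.1.2 and the Summary.

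This changes wording only. No new data are needed, because deaths from any cause already follow expedited reporting (Table 6-4). The downside is that an occasional truly unrelated early death will be counted, making the rate slightly less favourable. Under the assumed additions above, power at n = 330 stays at 96.6% or more.

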1.0 INTRODUCTION

1.1 Background

Atrial fibrillation (AF) is the most common sustained arrhythmia in humans. It affects anywhere from 0.4% to 1% of the general population, and increases in prevalence with age, from < 1% in young adults to 8% in patients over 80 years of age.^{1,2} AF is a complex, progressive disease that results in structural and electrical remodeling in the heart. In 2006, a 3-category classification system was established to distinguish and standardize the different levels of AF:³

- Paroxysmal: 2 or more AF episodes that terminate spontaneously within 7 days;
- Persistent (PsAF): AF sustained beyond 7 days or lasting less than 7 days but necessitating termination by intervention; and
- Longstanding persistent: AF greater than one year's duration.

The 2012 HRS/EHRA/ECAS Consensus Statement on catheter and surgical ablation recommended that patients be categorized by their most frequent pattern of AF during the six months prior to ablation.⁴ The 2006 ACC/AHA/ESC AF Management guidelines include the recommendation that catheter ablation be considered in persistent AF patients who are severely symptomatic after failure of one or more AADs plus rate control.³

Radiofrequency (RF) catheter ablation has provided excellent results for treating many types of supraventricular arrhythmias.^{1,5} Its utility in treating paroxysmal AF has already been established; studies have shown high rates of elimination of the arrhythmia.^{6,7} In a randomized clinical trial comparing catheter ablation to AAD therapy, RF ablation with the NAVISTAR® THERMOCOOL® catheter was associated with elimination of symptomatic atrial arrhythmias in 70% of patients, and elimination of any atrial arrhythmia irrespective of symptoms in 63% of patients at 1 year.⁷ One of the goals of the present study is to extend these findings in the persistent AF population. The 2012 HRS/EHRA/ECAS Consensus Statement notes that there have been no prospective multicenter randomized clinical trials of ablation versus antiarrhythmic drug therapy that have precisely defined the outcomes of AF ablation in patients with persistent AF or longstanding persistent AF.⁴ However, some of the electrical atrial remodeling may be reversible by destroying the foci.⁸ Studies that included a persistent AF sample have shown some improvement with PV isolation, although the rates of clinical efficacy were found to be lower in subjects with persistent AF than in those with paroxysmal AF at five,⁹ ten,⁸ or twelve^{10,11} months post ablation. A recent meta-analysis corroborated these findings with even longer follow-up times after a single ablation procedure, although due to between-study heterogeneity, the difference between AF types did not reach significance.¹² Many of the non-paroxysmal subjects among the included studies required multiple procedures to achieve long-term rhythm control.¹²

The 2012 HRS/EHRA/ECAS Consensus Statement states that electrical isolation of the pulmonary veins (PVs) from the left atrium is “the cornerstone for most AF ablation procedures.”⁴ However, in patients with persistent AF, more extensive ablation, based on linear lesions or complex fractionated electrograms, should be considered.⁴ In such patients, inclusion of the atrial myocardium becomes more important, as atrial remodeling occurs, augmenting the number of AF drivers and shifting their locations away from the PV ostia⁴ so that the PVs become less important as AF progresses from paroxysmal to persistent.⁹ The current study will utilize a “PVI + Triggers” approach, where isolation of all PVs will be performed, followed by ablation of “non-PV triggers” and triggers induced by isoproterenol. Additional ablation sites will be allowed at the discretion of the investigator but will be limited to certain parameters. All linear lesions will require confirmation of block by mapping or pacing maneuvers and prophylactic ablation of empirical sites is not recommended.

[REDACTED]

Animal studies have demonstrated that, during RF application at high power, saline irrigation maintains a low electrode-tissue interface temperature resulting in deeper and larger lesions.¹³ However, the first catheters that were introduced did not provide the same irrigation flow for any orientation of the catheter, and required increasing volumes of saline to be delivered with increasing number of RF applications. [REDACTED]

[REDACTED]

There have been several studies showing that there is a correlation between electrode-tissue contact and RF lesion generation.¹⁸⁻²⁰ Until recently, there has been no reliable mechanism

to provide a measurement of the direct CF between the tip of the RF ablation catheter and the endocardial tissue. [REDACTED]

[REDACTED]

